### **7.1.1. Packaging and Labelling**

LY3074828 will be supplied to the investigator by Lilly. Clinical trial materials are manufactured in accordance with good manufacturing practices. All investigational products will be stored, inventoried, reconciled, and destroyed according to applicable regulations.

LY3074828 is supplied for clinical trial use as lyophilized powder in a glass vial and should be stored in refrigerated conditions (2°C to 8°C). The vial is manufactured to deliver CCI of LY3074828 and will be reconstituted with CCI. Placebo will be normal saline (0.9% sodium chloride).

When reconstituted and in a syringe, LY3074828 cannot be distinguished visually from placebo.

Detailed instructions regarding supplies and preparation and handling of LY3074828 will be provided by the sponsor.

Clinical trial materials will be labeled according to the country's regulatory requirements.

## **7.2. Method of Treatment Assignment**

Subjects who meet all criteria for enrollment will be randomized to double-blind treatment at Visit 2. Assignment to treatment groups will be determined by a computer-generated random sequence using an interactive web-response system (IWRS), and then the site will be responsible for administering the treatment to the subjects.

To achieve between-group comparability for exposure to previous biologic therapy, the randomization will be stratified by prior exposure to biologic therapy for psoriasis (yes/no).

### **7.2.1. Timing of Doses**

The actual time of all dose administrations will be recorded in the subject's electronic case report form (eCRF).

## **7.3. Blinding**

This is a double-blind study during the induction period. Baseline dose cohort assignment will remain blinded throughout the study; however, during the maintenance period, dosing strategy (PRN or Q8W) will be open label. To preserve the blinding of the study, a minimum number of Lilly personnel will see the randomization table and treatment assignments before the study is complete. Only a study site pharmacist or other trained person will be unblinded at the site for investigational product preparation.

Emergency unblinding for AEs may be performed through the IWRS, which may supplement or take the place of emergency codes generated by a computer drug-labeling system. This option should be used ONLY if the subject's well-being requires knowledge of the subject's treatment assignment. All notifications resulting in an unblinding event are recorded and reported by the IWRS.

In case of an emergency, the investigator has the sole responsibility for determining if unblinding of a subject's treatment assignment is warranted. Subject safety must always be the first

consideration in making such a determination. If the investigator decides that unblinding is warranted, the investigator should make every effort to contact the Lilly clinical research physician (CRP) prior to unblinding a subject's treatment assignment unless this could delay emergency treatment of the patient. If a subject's treatment assignment is unblinded, Lilly must be notified immediately.

#### **7.4. Dosage Modification**

Dose adjustments are not permitted in this study, except for those for rescue therapy in the maintenance treatment period as described in Section 7.8.2.

#### **7.5. Preparation/Handling/Storage/Accountability**

Detailed instructions regarding supplies and preparation and handling of LY3074828 will be provided by the sponsor.

#### **7.6. Treatment Compliance**

Every attempt will be made to select subjects who have the ability to understand and comply with study instructions. The investigator is responsible for discussing methods to ensure high treatment compliance with the subject before randomization.

All doses of study medication will be administered at the study site. Deviation(s) from the prescribed dosage regimen should be recorded in the eCRF.

If a subject is noncompliant with study procedures and/or investigational product administration, the investigator should assess the subject to determine the reason for noncompliance and educate and/or manage the subject as appropriate to improve compliance. If, in consultation with Lilly or its designee, the noncompliance is deemed to be significant or if further noncompliance occurs, the subject should be discontinued from the study. A subject will be considered significantly noncompliant if he or she fails to attend for administration of study medication within the required treatment window as defined in the Schedule of Activities (Section 2).

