Vital signs (BP and heart rate), body temperature only if clinically indicated	X	X	X	X	X	X	X	X	X	X	X	Sitting blood pressure and pulse, to be obtained at approximately the same time as ECG measurements or blood sampling. When multiple assessments are scheduled for the same time point, the order of completion should be as follows: ECG, vital signs, and then blood sampling.
ECGs									X			ECGs should be performed before any blood is drawn. Subjects should be supine for approximately 5 to 10 minutes before ECG collection and remain supine but awake during ECG collection.
C-SSRS	X	X	X	X	X	X	X	X	X	X	X	
CCI												

Maintenance Dosing Period (Visits 8-18)												
Visit No.	V8	V9	V10	V11	V12	V13	V14	V15	V16	V17	V18	Comments
Week Relative to Study Drug Start	20	24	28	32	36	40	44	48	52	56	60	All activities should be completed prior to any study dose administration unless otherwise stated below.
Day with Visit Tolerance Interval	140 ± 5	168 ± 5	196 ± 5	224 ± 5	252 ± 5	280 ± 5	308 ± 5	336 ± 5	364 ± 5	392 ± 5	420 ± 5	
Study drug dosed	X	X	X	X	X	X	X	X	X	X	X	Subjects assigned to PRN will be evaluated at every visit to determine if dose needed. Subjects assigned to Q8W will get dosed on odd number visits.
Clinical Efficacy												
PASI	X	X	X	X	X	X	X	X	X	X	X	
sPGA	X	X	X	X	X	X	X	X	X	X	X	
PSSI, if applicable	X	X	X	X	X	X	X	X	X	X	X	Once a subject experiences symptoms related to scalp involvement, this form should be completed at all remaining indicated visits.
Whole body photographs				X					X			If subject has agreed to whole body photographs.
Health Outcomes												
PSS				X					X			
PatGA				X					X			
DLQI				X					X			In addition to the marked visits, DLQI also taken at PRN dosing or rescue treatment visits.
SF-36				X					X			
Laboratory Tests												
Hematology	X	X	X	X	X	X	X	X	X			Unscheduled blood chemistry and hematology panels may be performed at the discretion of the investigator.
Lymphocyte subsets									X			

Maintenance Dosing Period (Visits 8-18)												
Visit No.	V8	V9	V10	V11	V12	V13	V14	V15	V16	V17	V18	Comments
Week Relative to Study Drug Start	20	24	28	32	36	40	44	48	52	56	60	All activities should be completed prior to any study dose administration unless otherwise stated below.
Day with Visit Tolerance Interval	140 ± 5	168 ± 5	196 ± 5	224 ± 5	252 ± 5	280 ± 5	308 ± 5	336 ± 5	364 ± 5	392 ± 5	420 ± 5	

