## 8. Discontinuation Criteria

### 8.1. Discontinuation from Study Treatment

#### 8.1.1. *Permanent Discontinuation from Study Treatment*

Discontinuation of the investigational product for abnormal liver tests **should be considered** by the investigator when a subject meets one of the following conditions after consultation with the Lilly designated medical monitor and consideration of the clinical status of the subject (including patients with Gilbert's syndrome):

- alanine aminotransferase (ALT) or aspartate aminotransferase (AST) >8X upper limit of normal (ULN)
- alanine aminotransferase or AST >5X ULN for more than 2 weeks
- alanine aminotransferase or AST >3X ULN and total bilirubin level (TBL) >2X ULN or prothrombin time >1.5X ULN
- alanine aminotransferase or AST >3X ULN with the appearance of fatigue, nausea, vomiting, right upper-quadrant pain or tenderness, fever, rash, and/or eosinophilia (>5%)
- alkaline phosphatase (ALP) >3X ULN
- alkaline phosphatase >2.5X ULN and TBL >2X ULN
- alkaline phosphatase >2.5 ULN with the appearance of fatigue, nausea, vomiting, right quadrant pain or tenderness, fever, rash, and/or eosinophilia (>5%)

Subjects who discontinue the investigational product early will continue in the study according to the Schedule of Activities (Section 2).

Investigational product is to be discontinued for patients who experience clinically significant systemic hypersensitivity events (such as anaphylaxis) following administration of investigational product.

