### 10.3.1.3. Missing Data Imputation

Analysis of categorical efficacy and health outcome variables will be assessed using a NRI method. Subjects will be considered a nonresponder for the NRI analysis if they do not meet the clinical response criteria or have missing clinical response data at the analysis time point. Randomized subjects without at least 1 postbaseline observation will also be defined as nonresponders for the NRI analysis.

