### 10.3.2.4. Treatment Compliance

Treatment compliance with investigational product will be summarized for subjects who enter the induction and maintenance periods. A subject will be considered significantly noncompliant if he or she fails to attend for administration of study medication within the required treatment window as defined in the Schedule of Activities (Section 2). Overall compliance with therapy is defined to be missing no more than 20% of the expected doses and not missing 2 consecutive doses. Proportions of subjects who demonstrate overall compliance during the induction period will be compared between treatment groups using Fisher's exact test.

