HBsAg	hepatitis B surface antigen
HBV	hepatitis B virus
HIV	human immunodeficiency virus
HRQOL	health-related quality of life
IB	Investigator's Brochure
ICF	informed consent form
ICH	International Conference on Harmonisation
IL	interleukin
interim analysis	An interim analysis is an analysis of clinical study data, separated into treatment groups, that is conducted before the final reporting database is created/locked.
IV	intravenous
investigational product	A pharmaceutical form of an active ingredient or placebo being tested or used as a reference in a clinical trial, including products already on the market when used or assembled (formulated or packaged) in a way different from the authorized form, or marketed products used for an unauthorized indication, or marketed products used to gain further information about the authorized form.
ITT	intention-to-treat: The principle that asserts that the effect of a treatment policy can be best assessed by evaluating on the basis of the intention to treat a subject (that is, the planned treatment regimen) rather than the actual treatment given. It has the consequence that subjects allocated to a treatment group should be followed up, assessed, and analyzed as members of that group irrespective of their compliance to the planned course of treatment.
IWRS	interactive web-response system
MCS	mental component summary
MMRM	mixed-effects for repeated measures
NRI	nonresponder imputation

Term	Definition
NRS	numeric rating scale
PASI	Psoriasis Area and Severity Index
PASI 50	50% improvement in PASI from baseline
PASI 75	75% improvement in PASI from baseline
PASI 90	90% improvement in PASI from baseline
PASI 100	100% improvement in PASI from baseline
PatGA	Patient's Global Assessment of Psoriasis
PCR	polymerase chain reaction
PCS	physical component summary
PK/PD	pharmacokinetics/pharmacodynamics
PPD	purified protein derivative
PRN	as needed
PRO/ePRO	patient-reported outcomes/electronic patient-reported outcome
PSS	Psoriasis Symptom Scale
PSSI	Psoriasis Scalp Severity Index
PUVA	psoralen plus ultraviolet A light therapy
Q8W	every 8 weeks
RNA	ribonucleic acid
SAE	serious adverse event
SAP	statistical analysis plan

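### Protocol Section 7.6 ties leaving the study to a dosing-window lapse with no minimum count, which conflicts with the protocol's own ITT principle and can turn observable outcomes into imputed non-responses

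*Protocol*

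**What the plan says.** **Protocol Section 7.6.** When a subject is noncompliant, the investigator should find the reason and "educate and/or manage the subject as appropriate to improve compliance". If, in consultation with the sponsor or its designee, "the noncompliance is deemed to be significant or if further noncompliance occurs, the subject should be discontinued from the study". The section closes with the definition: "A subject will be considered significantly noncompliant if he or she fails to attend for administration of study medication within the required treatment window". After baseline, the dosing-visit windows in the Schedule of Activities are ±5 days.

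**Protocol Section 8.1.1.** "Subjects who discontinue the investigational product early will continue in the study according to the Schedule of Activities".

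**Protocol Section 10.3.2.4 and SAP Section 6.7.** Both repeat the Section 7.6 definition of significant noncompliance, without any consequence for study participation. They then add a second measure: "Overall compliance with therapy is defined to be missing no more than 20% of the expected doses and not missing 2 consecutive doses".

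**Protocol Appendix 1, ITT entry.** Subjects allocated to a group "should be followed up, assessed, and analyzed as members of that group irrespective of their compliance to the planned course of treatment".

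**Protocol Section 10.3.1.3 and SAP Section 6.3.1.** For categorical endpoints, subjects who "have missing clinical response data at the analysis time point" count as nonresponders.

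**Protocol Section 8.2.** Noncompliance is not named among the possible reasons for leaving the study, although investigator decision is. Early leavers have the Visit 804 procedures when they leave.

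**The concern.** Section 7.6 makes a dosing-attendance lapse a route out of the study, not only off the drug. Its definition has no threshold, so little is left to be deemed in the consultation, and sites may apply the section differently. A subject who stops the drug altogether stays under observation by Section 8.1.1, while a subject who attends late for one dose may be withdrawn.

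The statistical cost is avoidable missing data. A removed subject has a PASI at exit but not at Week 16, 52 or 104, so NRI records a failure that could have been an observed outcome. Continuous endpoints are not imputed this way; under MMRM the later values are simply missing. Safety observation stops after the Visit 804 assessment, which does include adverse events, laboratory tests and ECG.

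**Working it through.** **Step 1. The plan's own figure.** SAP Section 5.2 assumes PASI 90 rates of 60% and 3%, with 50 subjects per arm and a two-sided Fisher's exact test at 0.05, and states power over 99%. Exact enumeration of all 51 × 51 outcomes gives 0.9999999, so the figure is reproduced.

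**Step 2. Week 16.** Only one post-baseline dose, at Week 8 (day 56 ± 5), precedes the Week 16 PASI. Let q be the share removed at that dose, equal in both arms. The documents do not give q, so the range is assumed. Active rate = 60% × (1 − q); difference = 57 points × (1 − q); responders recoded per 50 active subjects = 50 × 0.60 × q.

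| q (assumed) | Active rate | Difference (points) | Responders recoded per 50 |
|---|---|---|---|
| 2% | 58.8% | 55.9 | 0.6 |
| 5% | 57.0% | 54.2 | 1.5 |
| 10% | 54.0% | 51.3 | 3 |
| 20% | 48.0% | 45.6 | 6 |
| 30% | 42.0% | 39.9 | 9 |

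Fisher power is still 0.9997 at q = 30%. The estimate shrinks in proportion to q, but the test is not threatened.

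**Step 3. Weeks 52 and 104, Q8W subjects.** The Schedule says "Subjects assigned to Q8W will get dosed on odd number visits". Visits 9 to 15 give 4 doses before Week 52 (Weeks 24 to 48). Visits 9 to 27 give 10 doses before Week 104 (Weeks 24 to 96). Let p be the out-of-window risk per dose (assumed), independent across doses, with every first lapse leading to removal. Share removed = 1 − (1 − p)^k.

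| p (assumed) | By Week 52 (k = 4) | By Week 104 (k = 10) |
|---|---|---|
| 1% | 3.9% | 9.6% |
| 2% | 7.8% | 18.3% |
| 5% | 18.5% | 40.1% |

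If removal is unrelated to response, the NRI response rate is the true rate times one minus the share removed. At Week 104 that factor runs from about 0.90 (p = 1%) to 0.60 (p = 5%).

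**Step 4. The two compliance measures side by side.** Weeks 16 to 104 hold 12 scheduled Q8W doses. One missed dose is 1/12 = 8.3%, and two non-consecutive misses are 2/12 = 16.7%. Both are within the 20% tolerance, yet the first miss already meets the definition of significant noncompliance. A dose given late is not a missed dose at all, and so fails only the window rule.

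**Step 5. Does the loss fall more on Q8W or on PRN?** This depends on what counts as a dosing window for a PRN subject. If only doses given count, and a subject has 2 (an assumption), removal is 1 − (1 − p)^2, or 2%, 4% and 10% at p = 1%, 2% and 5%. The Schedule, however, has PRN subjects evaluated for dosing at every maintenance visit. If attendance at each of those counts, there are 21 visits in Weeks 20 to 100, and 1 − (1 − p)^21 gives 19%, 35% and 66%. The first reading puts PRN below Q8W and the second puts it above.

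**The case against.** The strongest reply is that removal is not automatic. Section 7.6 asks for assessment and education first, has significance deemed with the sponsor, and says that the subject should, not must, be discontinued. Its alternative trigger, further noncompliance, would have no purpose if one late dose always ended participation. This stands. It makes the Step 3 figures an upper case for each assumed p. It also shows that the section is unclear within itself, since the definition that follows has no threshold.

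Other parts of the reply also stand:

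- Section 8.1.1 covers subjects who stop the drug and does not say that nobody may leave the study for noncompliance. It is in tension with Section 7.6, not in contradiction.
- The ITT population in Section 10.2 is not contradicted, because removed subjects stay in the denominator. The conflict is with the follow-up wording in Appendix 1.
- The 20% measure is a reporting summary with no discontinuation rule attached.

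A reader might also infer that the rule biases the maintenance results against Q8W relative to PRN. The documents do not support that. Step 5 shows that the direction depends on an unstated reading. The groups are formed by Week 16 response, not by randomization: PRN subjects are PASI 90 responders, while Q8W subjects are non-responders plus all placebo subjects. Although Section 5.4 speaks of comparing the two strategies, the planned maintenance summaries are descriptive, by treatment.

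**Conclusion.** The point holds as a conflict within the protocol that can create avoidable missing data. Read literally, one out-of-window dose can lead to leaving the study, against the Appendix 1 principle of follow-up irrespective of compliance. The primary comparison is not at risk: power stays above 99% at every assumed removal rate up to 30%, although the estimated response rate is pulled down in proportion. Binary endpoints at Weeks 52 and 104 are more exposed, with about 4% to 19% and 10% to 40% of Q8W subjects removed at an assumed 1% to 5% per dose. Those figures rest on independence across doses and on removal at every first lapse. The documents give no out-of-window rate, so the actual loss could be much smaller. No direction of bias between Q8W and PRN follows. The change is worth making because it is cheap and specific, but the point does not undermine the trial's main conclusion.

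**What to change.** Reconcile Protocol Sections 7.6, 8.1.1, 8.2 and 10.3.2.4, Appendix 1 and SAP Section 6.7 so that compliance with dosing is handled separately from study follow-up. Outcome collection at Weeks 16, 52 and 104, and the scheduled safety visits, should then be consistent with the Appendix 1 ITT principle. Out-of-window doses should be recorded as deviations, which Section 7.6 already asks for in the eCRF. The amendment should also say how the definition of significant noncompliance relates to the 20% and two-consecutive-dose measure, and whether a PRN visit with no dose due counts as a dosing window. Whether dosing continues after a lapse is a clinical decision for the sponsor, and nothing is proposed on it here.

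The cost is a few sentences in a protocol amendment with a matching SAP edit. Some subjects will stay in follow-up who would otherwise have left.

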#### **7.7. Concomitant Therapy**

All concomitant medication taken during the study must be recorded on the concomitant medication eCRF.

All subjects should maintain their usual medication regimens for concomitant conditions or diseases throughout the study unless those medications are specifically excluded in the protocol.

Subjects taking concomitant medications should be on stable dosages at the time of baseline and should remain at stable dosages throughout the study unless changes need to be made because of AEs. Additional systemic drugs are to be avoided during the study, unless required to treat AEs. Other medications may be allowed if they are approved by the sponsor or its designee.

Uses of nonlive (inactivated) vaccinations are allowed for all subjects. Use of live, attenuated vaccines is prohibited.

Concomitant therapies for treatment of psoriasis during the study are permitted only as outlined in [Table AMAF.4](#).

**Table AMAF.4.**

CCI [REDACTED]

[REDACTED]	[REDACTED]	[REDACTED]	[REDACTED]
[REDACTED]	[REDACTED]	[REDACTED]	[REDACTED]
[REDACTED]	[REDACTED]	[REDACTED]	[REDACTED]
[REDACTED]	[REDACTED]	[REDACTED]	[REDACTED]

## 7.8. Treatment after the End of the Study

### 7.8.1. Continued Access

LY3074828 will not be made available to subjects after conclusion of the study except by consenting and being eligible to participate in the separate long-term extension study, as described in Section [7.8.3](#).

### 7.8.2. Special Treatment Considerations

Subjects in the maintenance PRN dosing arm may receive blinded rescue treatment with 300 mg Q8W. Rescue treatment may occur if not regaining a PASI  $\geq 90$  after 3 consecutive doses of retreatment or if a subject is below a PASI 50 following 1 retreatment dose. A subject starting rescue treatment will remain on that regimen through the end of the study regardless of any subsequent changes in PASI score.

All biological agents carry the risk of an injection site and/or hypersensitivity general reaction. Therefore all subjects should be closely monitored for signs or symptoms that could result from such reactions. Sites should have appropriately trained medical staff and appropriate medical equipment available when subjects are receiving study drug. If a subject experiences an acute hypersensitivity reaction after an injection of study drug, he or she should receive appropriate supportive care.

### 7.8.3. Separate Long-Term Extension Study

Subjects who complete Study AMAF through the end of the maintenance period (Week 104 [Visit 29]) may be eligible to participate in a separate long-term extension study, which offers an additional treatment with LY3074828, pending competent authority and/or ERB approvals for the separate long-term extension study. To be eligible for the separate long-term extension study, subjects enrolled in Study AMAF must not have been permanently discontinued from the study treatment or from the study itself. Furthermore, subjects must meet the enrollment criteria specified in the protocol for the separate long-term extension study. Subjects who do not enroll into the separate long-term extension study will complete the follow-up period of Study AMAF.

## 8. Discontinuation Criteria

### 8.1. Discontinuation from Study Treatment

#### 8.1.1. *Permanent Discontinuation from Study Treatment*

Discontinuation of the investigational product for abnormal liver tests **should be considered** by the investigator when a subject meets one of the following conditions after consultation with the Lilly designated medical monitor and consideration of the clinical status of the subject (including patients with Gilbert's syndrome):

- alanine aminotransferase (ALT) or aspartate aminotransferase (AST) >8X upper limit of normal (ULN)
- alanine aminotransferase or AST >5X ULN for more than 2 weeks
- alanine aminotransferase or AST >3X ULN and total bilirubin level (TBL) >2X ULN or prothrombin time >1.5X ULN
- alanine aminotransferase or AST >3X ULN with the appearance of fatigue, nausea, vomiting, right upper-quadrant pain or tenderness, fever, rash, and/or eosinophilia (>5%)
- alkaline phosphatase (ALP) >3X ULN
- alkaline phosphatase >2.5X ULN and TBL >2X ULN
- alkaline phosphatase >2.5 ULN with the appearance of fatigue, nausea, vomiting, right quadrant pain or tenderness, fever, rash, and/or eosinophilia (>5%)

Subjects who discontinue the investigational product early will continue in the study according to the Schedule of Activities (Section 2).

Investigational product is to be discontinued for patients who experience clinically significant systemic hypersensitivity events (such as anaphylaxis) following administration of investigational product.

